1.2 SCHEMA

1.3 SCHEDULE OF ACTIVITIES

	Pre-screening (Pre-consent)	Visit 1 Day 1	Visit 2 Day 63 ±52	Visit 3 Day 70 ±50
Review Eligibility	X			
Informed Consent		X		
Demographics		X		
Clinical history		X		
TMS & MRI compatibility		X		
Height & Weight		X		
MRI and Resting State Scans		X		
Outcome Evaluation				
Need for Cognition Scale			X	
Working Memory performance			X	X
Effort Discounting			X	X
Long-range temporal correlations			X	X

	Pre-screening (Pre-consent)	Visit 1 Day 1	Visit 2 Day 63 ±52	Visit 3 Day 70 ±50
Avalanche branching statistics			X	X
Functional E/I balance			X	X

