4 STUDY DESIGN

4.1 OVERALL DESIGN

The hypothesis to be studied in this Trial is that criticality in the brain depends on the balance of cortical excitation to inhibition and that sub-criticality impacts on working memory and subjective cognitive effort. This hypothesis leads to predictions including that TMS protocols which decrease the cortical excitation to inhibition ratio (like theta burst stimulation) will make the brain more sub-critical. In turn, when theta-burst stimulation is targeted at regions involved in working memory like the dorsolateral prefrontal cortex, this predicts worse, more inflexible working memory performance and greater subjective effort when people are engaged in working memory tasks.

We will use a repeated measures design wherein every subject is their own control. Specifically, on different days, separated by at least one week, participants will receive continuous theta burst stimulation to either their dorsolateral prefrontal cortex (the active condition) or the angular gyrus (the control condition). The order of these sessions is pseudo-randomized across participants. Specifically, 15 of our target 30 participants will be randomly pre-assigned to complete an active condition session first and control condition second and vice versa for the other 15 participants. The pre-assignment will be determined by permutation of a list of subject numbers before recruitment starts. Every subject number will subsequently be assigned to participants in order of their recruitment. Errors in randomization will be documented and session order will be included as a covariate in all analyses.

Participants will come in for three sessions: 1) a first session to complete paperwork and an MRI structural scan for subsequent neuronavigation and a resting state scan, 2) one counterbalanced order session for dorsolateral prefrontal cortex stimulation and working memory task performance and 3) another counterbalanced order session for angular gyrus stimulation and working memory task performance. The first stimulation session can happen the day after an MR scan (but no more than 113 days after the MR

scan) and the second stimulation session can happen one week after the first stimulation session (but no more than 113 days after the first stimulation session).

This is a single-site trial.

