7.2 PARTICIPANT DISCONTINUATION/WITHDRAWAL FROM THE STUDY

Participants are free to withdraw from participation in the study at any time upon request.

An investigator may discontinue a participant from the study for the following reasons:

- Identification of brain abnormalities during the MRI scan
- Non-compliance with regards to cognitive task instructions
- Lost-to-follow up; unable to contact subject (see **Section 7.3, Lost to Follow-Up**)
- Any event or medical condition or situation occurs such that continued collection of follow-up study data would not be in the best interest of the participant or might require an additional treatment that would confound the interpretation of the study; With TMS an unlikely but possible medical condition would be onset of a seizure
- The participant meets an exclusion criterion (either newly developed or not previously recognized) that precludes further study participation

The reason for participant discontinuation or withdrawal from the study will be recorded on the Case Report Form (CRF). Subjects who sign the informed consent form and are randomized but do not receive the study intervention may be replaced. Subjects who sign the informed consent form, and are randomized and receive the study intervention, and subsequently withdraw, or are discontinued from the study, will be replaced.

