8.3.3.3 EXPECTEDNESS

A clinician with appropriate expertise in transcranial magnetic stimulation will be responsible for determining whether an adverse event (AE) is expected or unexpected. An AE will be considered unexpected if the nature, severity, or frequency of the event is not consistent with the risk information previously described for the study procedures.

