8.3.4 TIME PERIOD AND FREQUENCY FOR EVENT ASSESSMENT AND FOLLOW-UP

The occurrence of an adverse event (AE) or serious adverse event (SAE) may come to the attention of study personnel during study visits and interviews of a study participant presenting for medical care, or upon review by a study monitor.

All AEs, not otherwise precluded per the protocol, will be captured on the appropriate case report form (CRF). Information to be collected includes event description, time of onset, clinician's assessment of severity, relationship to study procedures (assessed only by those with the training and authority to make a diagnosis), and time of resolution/stabilization of the event. All AEs occurring while on study will be documented appropriately regardless of relationship. All AEs will be followed to adequate resolution.

Any medical or psychiatric condition that is present at the time that the participant is screened will be considered as baseline and not reported as an AE. However, if the study participant's condition deteriorates at any time during the study, it will be recorded as an AE.

Changes in the severity of an AE will be documented to allow an assessment of the duration of the event at each level of severity to be performed. Documentation of onset and duration of each episode will be maintained for AEs characterized as intermittent.

The Principal Investigator will record events with start dates occurring any time after informed consent is obtained until 7 (for non-serious AEs) or 30 days (for SAEs) after the last day of study participation. At each study visit, the investigator will inquire about the occurrence of AE/SAEs since the last visit. Events will be followed for outcome information until resolution or stabilization.

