8.3.7 REPORTING EVENTS TO PARTICIPANTS

Incidental findings related to the structural MRI scans are possible. MRIs are collected by the Brown MRF (Magnetic Resonance Facility) and staff MD who will review the images for any reportable anomalies and contact participants directly if any are identified.

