10.1.6 SAFETY OVERSIGHT

Safety Monitoring

Participants will be monitored for adverse events by study staff. Significant as well as mild adverse effects of TMS stimulation (seizures, headache) and MRI scanning (claustrophobic reaction, and movement of ferromagnetic objects) will be monitored through questionnaires (e.g. TMS monitoring questionnaire) before and after each TMS and MRI session.

Risk mitigation plan and Trial stopping rules

Three outcomes will be monitored throughout the study as safety endpoints associated with a stop rule.

1. **Number of TMS-induced seizures:** As described above, we will track TMS-induced seizures and clinically significant adverse events requiring outside evaluation. Each stop rule is described in detail below:
 - a. More than 1 TMS-induced seizure resulting in hospitalization within any 10 consecutive participants who receive TMS will result in a protocol hold until further evaluation by the PI and Co-Sponsor [name]. [name] has extensive experience with

TMS and overseas safety and training compliance at Brown's TMS facility. We will also consult [name], M.D., Professor of Psychiatry and Human Behavior at the Alpert Medical School of Brown University, founding Section Chief of Psychiatric Neuromodulation at VA Providence, and Lead for Mental Health Research at the VA RR&D Center for Neurorestoration and Neurotechnology. [name] possesses the necessary clinical expertise to evaluate the proposed safety endpoints. No new TMS sessions will be administered to any participant once this stop rule is enacted until evaluation of the events is concluded and it is deemed appropriate to proceed. However, participants who have completed their TMS treatments may be scheduled for follow-up visits.

- 2. Clinically significant adverse events (i.e. adverse events that require referral for further evaluation) likely related to TMS.** For example, a mild headache after TMS that resolves spontaneously or with over-the-counter medication will not be considered clinically significant. A severe headache that starts during or shortly after TMS and fails to resolve with time and/or OTC intervention would prompt referral to an Emergency Department and will be considered clinically significant.

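### First cTBS may be given the day after the MRI, before the planned medical review of the images need be finished or known to the investigator

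*Protocol*

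**What the plan says.** Four places in the protocol bear on the order of scan, image review and stimulation.

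- **Timing, section 4.1.** "The first stimulation session can happen the day after an MR scan". The latest permitted first stimulation is 113 days after the scan.
- **Timing, section 1.3.** The Schedule of Activities puts the scan at Visit 1 on Day 1 and the first stimulation at "Visit 2 Day 63 ±52".
- **Image review, section 8.3.7.** The scans are made at the university's MR facility, with a "staff MD who will review the images for any reportable anomalies and contact participants directly if any are identified". The section gives no time by which this is done and does not say that the investigator is told.
- **Use of a finding, section 7.2.** One of the reasons for which the investigator may discontinue a participant is "Identification of brain abnormalities during the MRI scan".

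Nothing in the protocol text at hand makes the first TMS session wait for the review in 8.3.7.

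**The concern.** The protocol already has all the parts of a safeguard: a structural scan before stimulation, a physician who looks at it, and a discontinuation reason that refers to it. It does not put them in order. The person who can act under 7.2 is the investigator, the person stated to receive the finding under 8.3.7 is the participant, and 4.1 lets stimulation go ahead the next day.

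What is at stake is participant safety. Section 2.3.1 describes the seizure risk of TMS as very small on two conditions: parameters within the consensus limits, and careful screening of participants. Section 2.3.3 counts a history of brain trauma among the risk factors to screen for. Apart from the scan, that screening rests on what participants report (5.5, 8.1), and a participant cannot report a lesion nobody has found. The scan is acquired for neuronavigation (2.3.3), but it is also the only direct look at the brain before stimulation.

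**Working it through.** There is no sample size, power or error rate to reproduce. The check is day arithmetic on the visit windows, followed by a comparison of the routes by which a finding could reach the investigator.

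**Step 1: earliest and latest first stimulation, with the scan on Day 1 (1.3).**

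| Source | Earliest | Latest | Interval from scan |
|---|---|---|---|
| 4.1 | 1 + 1 = Day 2 | 1 + 113 = Day 114 | 1 to 113 days |
| 1.3 | 63 − 52 = Day 11 | 63 + 52 = Day 115 | 10 to 114 days |

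The two sources disagree by nine days on the earliest date.

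**Step 2: how long stimulation is permitted before the review is done.** The protocol states no review time, so let T be the number of days from scan to completed review and g the minimum interval from Step 1. The number of days on which stimulation is permitted before the review is max(0, T − g). The days left in the 4.1 window after the review are 113 − T. The values of T below are assumptions, chosen to show a range.

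| Assumed T (days) | Permitted days before review, 4.1 (g = 1) | Permitted days before review, 1.3 (g = 10) | Days left of 113 |
|---|---|---|---|
| 2 | 2 − 1 = 1 | 0 | 113 − 2 = 111 |
| 7 | 7 − 1 = 6 | 0 | 113 − 7 = 106 |
| 14 | 14 − 1 = 13 | 14 − 10 = 4 | 113 − 14 = 99 |

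Under 4.1, any review longer than one day leaves some exposure. Under the Schedule, only a review longer than ten days does. With no stated limit on T, neither window guarantees that the review comes first.

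**Step 3: routes to the investigator.**

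- *Section 8.3.7* sends the finding to the participant. No onward report is stated.
- *Section 8.3.4* provides an inquiry: "At each study visit, the investigator will inquire about the occurrence of AE/SAEs since the last visit". It asks about adverse events, and the same section says that a "condition that is present at the time that the participant is screened will be considered as baseline and not reported as an AE". A pre-existing anomaly would fall under that exception. The inquiry also helps only if the review is finished and the participant mentions the result.
- *Section 10.1.6* uses questionnaires before and after sessions, but the MRI items it names are reactions to the scanner: "MRI scanning (claustrophobic reaction, and movement of ferromagnetic objects) will be monitored through questionnaires". Image findings are not among them.
- *Section 6.2.1* has the operators, one of whom is the principal investigator, use each participant's structural scan for neuronavigation. They therefore handle the images before stimulating, independently of the 8.3.7 review. This is targeting and not a medical read.
- *Sections 5.1 and 5.2* require a neurologically normal participant and exclude earlier brain injury. These criteria could cover some findings, but only once the investigator knows of them.

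No stated route ensures that the result of the medical review reaches the investigator before the first stimulation.

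**The case against.** The strongest reply is that the sections do not contradict each other. The scan is for targeting, no eligibility criterion requires a normal MRI, and 7.2 is permissive and can still be used between the two stimulation sessions. Section 8.3.7 concerns reporting to participants, so its silence about the investigator is weak evidence that no report is made. The wording of 7.2 could also cover something noticed at the scanner. Reading times and reporting lines may be set out in facility procedures or the consent form, neither of which was available, and 2.3.3 does refer to facility procedures for implanted objects and devices.

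Much of this stands as a limit on the point. A reader might infer that the protocol sets an MRI clearance and then breaches it, or that the investigator would never learn of a finding. The documents support neither: the 7.2 reason is discretionary, and indirect routes exist. Nor is there a basis for saying how often abnormalities would be found in this healthy sample, or how much risk cTBS would add.

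The objection does not remove the problem of order. The next-day permission in 4.1 is an explicit rule, and following it can put stimulation ahead of a review that the protocol itself plans. Being able to discontinue after the first session does not help for that session. The protocol does not refer to facility procedures for this step.

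**Conclusion.** The point holds as a safety gap in sequence and communication, worth correcting in the protocol; it is not something an analysis plan would settle. As written, the first cTBS may be given before the investigator is in a position to use the MRI reason in 7.2. The minimum interval is 1 day under 4.1 or 10 days under 1.3, with no stated limit on the review.

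The day counts in the table depend on assumed review times. If the Schedule governs, two of the three assumed times give no exposure, and a short turnaround under facility procedures could close the timing part altogether. The absence of a stated report to the investigator would remain. The conclusion also assumes that the 8.3.7 review is the only medical read of the images, since no other is described.

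It might seem to follow that a TMS-experienced clinician should clear every finding. The protocol does not support going that far: section 8.3.3.3 says "A clinician with appropriate expertise in transcranial magnetic stimulation will be responsible", but for judging whether an adverse event is expected. Clearance of images would be a new duty, and it is not needed to close this gap.

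**What to change.** 1. State in 4.1 and 8.3.7 that the first TMS session is not held until the facility physician's already planned review of the structural scan is complete and any reportable anomaly has been passed to the investigator, with the participant's agreement if that is needed. The investigator can then apply 7.2 before stimulation.
2. Give one earliest day for Visit 2 in both 4.1 and the Schedule of Activities.

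The cost is a wording amendment, one added communication from the facility to the investigator, and possibly some days' delay to the first stimulation visit. The delay fits the window: even at the assumed 14 days, 99 of the 113 days remain. A first session on Day 15 (1 + 14) plus the one-week separation gives Day 22 for the second, well before the latest Visit 3 day of 70 + 50 = Day 120.

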We may apply rTMS in patterned bursts, using continuous theta-burst stimulation (cTBS) for up to 40 s offline followed by a second train after a timed delay (for a total of 1200 pulses). The pattern consists of bursts of three rapid (50 Hz) pulses delivered at a frequency of 5 Hz. In a “spaced” variant of this procedure, two trains are delivered, with a 5-15 minute break in between trains. The spaced variant is advantageous in that it produces more consistent and reliable effects on cortical E/I balance in a meta-analysis (Chung et al. 2018). Importantly, a spaced variant is deemed safe, conforming to the standards articulated in a consensus statement (Rossi et al. 2020). While spaced TBS procedures increase the overall pulse count, they do not increase stimulation intensity or frequency which are of primary concern. At present, spaced TBS procedures with higher pulse counts have been used safely in dozens of studies and hundreds of participants without incident.

Offline TBS has been shown to be effective at eliciting both disruptive and facilitative effects during tasks related to cognitive control and learning. Prior work has shown that TBS effects can last up to 60 minutes following stimulation (Opie et al., 2017; Tse et al., 2018). During this time participants will remain in the lab as the stimulation would be applied in the beginning of the experimental session. This offline technique provides a means of testing the necessity of a brain region for a given task while controlling for the potentially distracting nature of the stimulation itself. It is of higher potency and lasts for a longer duration than other forms of offline stimulation, yet it uses lower intensities and for shorter total durations of stimulation.

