The intervention is spaced, continuous theta burst (cTBS) stimulation to either the anatomically-defined dorsolateral prefrontal cortex or angular gyrus. This will entail two trains of 50 Hz triplet bursts of stimulation delivered at 5 Hz (theta rhythm) continuously for 40 seconds (600 pulses for each train for a total of 1200 pulses) at an intensity based on 80% of a participant's active motor threshold. These two trains will be separated by between 5 and 25 minutes of rest, hence the stimulation is "spaced".

Subjects will be their own controls. The use of subjects as their own controls was selected because it will permit within-participant comparisons of the effect of theta burst stimulation on the dorsolateral prefrontal cortex versus the angular gyrus. While this approach will avoid many random individual difference factors which might confound interpretation of effects relative to a between-participants design, the chief limitation of this design is session order effects. Namely every participant will have target stimulation occurring either first, or after a control stimulation session, and they will also perform the working memory tasks either first, or after another session. Session order will be treated as a covariate in all analyses.

The only stratification among participants is gender. There are no expected effects of this stratification.

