4.3 JUSTIFICATION FOR INTERVENTION

There are few tools for causally manipulating the cortical balance of excitation to inhibition in humans. TMS was chosen as an intervention for modulating E/I balance in the dorsolateral prefrontal cortex to alter critical dynamics with consequences for working memory and subjective cognitive effort. Transcranial magnetic stimulation has already been shown to modulate cortical E/I balance, with effects on working memory performance when targeting the dorsolateral prefrontal cortex. It is widely used, safe

and effective. While there are pharmacological means of modulating E/I balance, it is impossible to selectively target the dorsolateral prefrontal cortex with pharmacological interventions.

A single train of 600 pulses of continuous theta burst stimulation (cTBS) is a standard cTBS design. We are using a modification involving two trains of 600 pulses separated by 5 to 25 minutes of rest in between based on a meta-analysis showing that the effects are more reliable and more durable for a spaced cTBS design relative to a single train cTBS (Chung et al. 2016).

We will require two separate stimulation sessions for participants so that we can compare the effects of stimulation on the target versus a control location. The sessions will be separated by at least one week providing sufficient time for normalization of brain function between sessions.

Both sessions are needed for a within-participants comparison of target versus control stimulation effects.

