6.1.2 ADMINISTRATION AND/OR DOSING

As noted, the intervention is spaced, cTBS to either (in alternate sessions) the anatomically-defined dlPFC or angular gyrus. Each session will thus entail two trains of 50 Hz triplet bursts of stimulation delivered at 5 Hz (theta rhythm) continuously for 40 seconds (600 pulses for each train for a total of 1200 pulses) at an intensity based on 80% of a participant's active motor threshold to either the target or control region. These two trains will thus constitute the full-dose intervention in either location.

Each participant will have their own personal set of two sessions and will thus not interact with other participants during the study.

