6.2 FIDELITY

6.2.1 INTERVENTIONIST TRAINING AND TRACKING

All TMS operators will receive training on the two key variables which may affect the consistency of cTBS. The first is the strength of stimulation intensity. Here, stimulation intensity will be based on participants' active motor threshold, which is diagnosed with the use of TMS-evoked potentials measured by electromyography and leads attached to participants' right hand, pursuant to a single pulse to their motor cortex hand knob. Motor thresholding will be based on a semi-automated threshold detection algorithm which is given feedback about the efficacy a given pulse for eliciting a motor evoked potential of 100 microvolts from peak to trough. Thus threshold identification should be standardized across participants, as should corresponding stimulation intensities.

The second degree of freedom is the precision of TMS targeting. For both motor threshold detection and cTBS, it is important to ensure precise targeting (of the hand knob and dlPFC, respectively). To ensure consistent targeting, we will use participant-specific structural MRI scans coupled with 3D vision-based neuronavigation systems. The neuronavigation system gives real-time feedback for precision targeting. Also, the exact location of every single pulse is recorded during stimulation, to ensure consistency. Finally, only two TMS operators will be used for the entirety of the study (the PI and one assistant), and both will be thoroughly trained to ensure consistent administration.

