6.3 MEASURES TO MINIMIZE BIAS: RANDOMIZATION AND BLINDING

All participants will complete both one target and one control stimulation session, but the order of these sessions will be pseudo-randomized. Specifically, participants will be assigned participant ID numbers based on their order of recruitment, but the participant ID numbers will be pseudo-randomized with respect to the order of target versus control stimulation sessions. Pseudo-randomization of IDs will be saved in a digital file and included in all subsequent analyses as a covariate of no interest. Any breaking of pseudo-randomization will be corrected with subsequent re-pseudo-randomization of unassigned ID numbers to ensure balance in session orders across participants. This pseudo-randomization will be managed / maintained by the PI.

The specific session that a participant is in (target versus control region) will be known to the experimenter (there is no way for the experimenter not to know since they are administering stimulation). To mitigate the impact on participants, they will be instructed that we will stimulate the brain on two different days, making no reference to possible differential effects across brain regions. The experimental condition will not be explained to the participant until the end of their participation, during debriefing.

Any instance of accidental unblinding – e.g. the participant learns that dlPFC stimulation is considered target, and angular gyrus is considered control stimulation will be noted and subsequent analysis will be conducted both including and excluding these participants to ensure that their inclusion has no effect on the conclusions of the study.

While it may be possible for some participants to infer that effects of stimulation at different sites should have differential effects, they will not be made aware which sites we expect to impact on working memory performance or subjective effort.

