9.1 STATISTICAL HYPOTHESES

- Primary Endpoint(s):

We predict that, relative to pre-stimulation rest, continuous theta burst stimulation (cTBS) will result in a reduction of the local balance of cortical excitation to inhibition as reflected in the functional E/I balance in proximity to stimulated targets.

We also predict that, relative to pre-stimulation rest, cTBS will result in a reduction in markers of critical dynamics (including, e.g., long-range temporal correlations) in proximity to stimulation targets.

Finally, we predict that, relative to angular gyrus stimulation, cTBS to the dorsolateral prefrontal cortex will increase subjective cognitive effort.

- Secondary Endpoint(s):

We hypothesize that subjective effort reflects divergence from a critical state and that criticality depends on the E/I balance. As such, we predict that there will be individual difference correlations in the degree to which TMS perturbs E/I balance, alters measures of criticality including long-range temporal correlations, and ultimately amplifies subjective effort.

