9.4.2 ANALYSIS OF THE PRIMARY ENDPOINT(S)

The following key outcomes will be assessed in this study. All measures are interval with the exception of the categorical covariate of sex.

- Subjective effort
 - Likert scale ratings (ranging from 1-10) of task-induced effort, demand, time pressure, and stress
 - subjective values as estimated from an indifference point discounting procedure
 - self-reported motivation to engage in demanding tasks on a set of Likert scales with continuous values ranging from 0-20
- E/I balance
 - fEI derived measure with exponents ranging approximately from 0.0-2.0
 - power-law exponents with exponents approximating -2.0
- Critical dynamics
 - Long range temporal correlations – a derived measure with exponents ranging approximately from 0.5-1.0
 - Avalanche size and duration distribution exponents approximating -2.0 and -1.5, respectively
- N-back working memory performance
 - overall accuracy rate as a percentage
 - median correct reaction times by trial type: lures versus targets versus regular trials
 - the discrimination index d'

Primary analyses of these outcomes will entail multiple regression models in which outcomes will be regressed on cTBS condition (target versus sham), controlling for sex and age.

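### The gap between the two cTBS trains has two stated ranges and need not match across a participant's sessions, which adds avoidable, probably small, noise to the between-site contrasts

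*Protocol*

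**What the plan says.** The protocol states the gap between trains in three places.

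- Section 4.1: "These two trains will be separated by between 5 and 25 minutes of rest".
- Section 4.3: "two trains of 600 pulses separated by 5 to 25 minutes of rest in between".
- Section 2.3.1, for the spaced variant: "two trains are delivered, with a 5-15 minute break in between trains".

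The sections where a matching rule might be expected do not contain one. Section 6.1.2 gives the pulse pattern, count and intensity and says "These two trains will thus constitute the full-dose intervention in either location", without naming a gap. Section 6.2.1 says "All TMS operators will receive training on the two key variables which may affect the consistency of cTBS"; the two are stimulation intensity and targeting. Section 6.3 deals with session order and blinding and does not mention the gap. It does acknowledge that the operator knows the site: "there is no way for the experimenter not to know since they are administering stimulation".

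The contrasts that depend on comparing the two sessions are the primary regression in 9.4.2, in which "outcomes will be regressed on cTBS condition (target versus sham), controlling for sex and age"; the prediction in 9.1 that "relative to angular gyrus stimulation, cTBS to the dorsolateral prefrontal cortex will increase subjective cognitive effort"; and the working-memory objective in section 3. The covariates named are session order (sections 3, 4.1 and 6.3), sex and age (9.4.1 and 9.4.2). The gap is not one of them.

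**The concern.** Spacing is the feature that sets this regimen apart from the standard single train, and 4.3 defends it on grounds of reliability and durability. Yet its length may vary fivefold, and it may differ between the two sessions that serve as each other's control. The design relies on within-person comparison to remove nuisance variation, and an unmatched delivery parameter puts some back.

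The stake is precision in the dlPFC versus angular gyrus contrasts. If the gap happened to follow the site, those contrasts would also be biased. The within-session pre-post comparisons in 9.1 and 9.4.1 are not confounded by a mismatch between sessions.

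Separately, the current text gives two upper limits for one procedure. An operator who follows 4.1 could use a 25-minute gap that the risk section does not describe.

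This is a matter for the protocol rather than for an analysis plan, because it concerns how the intervention is delivered.

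**Working it through.** **Inputs from the protocol.** Gap of 5 to 25 minutes (4.1, 4.3) or 5 to 15 minutes (2.3.1); 30 participants, alpha 0.05, and 80% power at d = 0.53 (9.2).

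**Largest mismatch for one participant.** Upper limit minus lower limit:
- 4.1 and 4.3: 25 − 5 = 20 minutes.
- 2.3.1: 15 − 5 = 10 minutes.

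This needs the shortest allowed gap in one session and the longest in the other.

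**Typical mismatch.** The protocol does not say how gaps will be chosen. Assume that they are independent and uniform over a range of width w in each session, which is pessimistic for two trained operators. Then the mean absolute difference is w/3, the SD of the difference is w/√6, and the probability of differing by more than 5 minutes is (1 − 5/w)².

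| Range | w | Mean absolute difference | SD of difference | P(more than 5 min) |
|---|---|---|---|---|
| 5–25 | 20 | 6.7 min | 8.16 min | 56% |
| 5–15 | 10 | 3.3 min | 4.08 min | 25% |

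**Difference carried into the contrast.** With gaps unrelated to site, the expected mean difference between sites is zero. Its standard error over 30 participants is 8.16/√30 = 1.5 minutes, or 4.08/√30 = 0.7 minutes under 5–15.

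**Power, baseline first.** A paired t-test with n = 30, 29 degrees of freedom and two-sided 0.05 (9.2 does not state sidedness) has power 80.1% at d = 0.53. This reproduces the 80% in 9.2.

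**Power, illustration.** The documents give no effect of gap on outcome, so assume that each 10 minutes of gap shifts the outcome by b SDs of the paired difference. The variance of the paired difference is multiplied by 1 + b²(SD/10)², and d is divided by the square root of that factor.

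| b (assumed) | 5–25: variance factor, d, power | 5–15: variance factor, d, power |
|---|---|---|
| 0.1 | 1.007, 0.528, 79.9% | 1.002, 0.530, 80.0% |
| 0.3 | 1.060, 0.515, 77.8% | 1.015, 0.526, 79.5% |
| 0.5 | 1.167, 0.491, 73.8% | 1.042, 0.519, 78.5% |

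Simulation with 200,000 trials per cell agreed to within 0.1 percentage point.

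**After matching.** If the two gaps agree within 2 minutes, with the difference uniform from −2 to 2, its SD is 4/√12 = 1.15 minutes. Power is then 80.0% to 80.1% for all three slopes.

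At d = 1.39, the other effect size in 9.2, the paired test has power above 99.9% in every case. That is not the 95% stated there, but the difference does not bear on this point.

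**The case against.** The strongest case against the point is that no consequence has been shown. The protocol treats 5 to 25 minutes as one regimen and gives no relation between gap length and any endpoint. Every power figure above rests on an assumed slope and an assumed distribution of gaps, and the largest loss needs the steepest slope together with the loosest timing. The d of 0.53 may also already include ordinary delivery variability, in which case inflating the variance counts it twice. All of this stands, and it is why the point is minor.

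A reader might infer that the site contrast is biased, because the operator is unblinded and free to set the gap. The documents do not support that. Unblinded delivery is unavoidable here, and nothing says that the gap will follow the site. Session order is pre-assigned 15 and 15, so a drift in gap from first to second session would not line up with site. What remains is that the protocol does not prevent a systematic difference and does not ask for the delivered gap to be recorded, so an imbalance might not be detectable afterwards.

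A reader might also take 20 minutes as the size of the confound. It is the extreme for a single participant, not the expected difference in the contrast.

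It can also be said that 2.3.1 is permissive risk text, that it already describes the delay as timed, and that a same-gap rule belongs in a session procedure. The first part is fair: the conflict between ranges is editorial, and the two design passages agree with each other. The second part is less persuasive. Sections 4.1 and 4.3 do state a rule for the gap, and it is looser than a within-person comparison needs.

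Finally, gap length is not the only loose timing. The interval from the second train to testing is not fixed either, so matching the gap alone would not equalise post-stimulation timing.

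**Conclusion.** The point holds as a cheap, minor improvement. Three facts are established from the text: two ranges for one procedure, no requirement that a participant's two sessions use the same gap, and no adjustment for it. The maximum mismatch for one participant is 20 minutes under 4.1 and 4.3, and 10 minutes under 2.3.1.

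The effect on the results cannot be measured from the documents. Under the assumed slopes with independent uniform gaps, the loss of power at d = 0.53 is 0.2 to 6.3 percentage points with 5–25 and 0.1 to 1.6 points with 5–15. The likely loss is small. Neither bias between sites nor a threat to the trial's conclusions can be claimed: bias would require gaps that differ systematically by site, and nothing in the protocol indicates that they will.

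**What to change.** In 4.1, add a sentence that the second stimulation session will repeat the gap used in that participant's first stimulation session, within about 2 minutes. The tolerance is a practical suggestion and does not come from the documents. The full range can still be used across participants.

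State one range in 2.3.1, 4.1 and 4.3. This correction is worth making even if the matching rule is declined.

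Record the delivered gap for each session. Optionally, repeat the 9.4.2 contrast with the within-participant gap difference as a covariate.

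The cost is one sentence, one aligned range and one recorded value per session. Section 2.3.1 already describes the delay as timed, so no extra equipment, staff or visits are needed. The downside is slightly less scheduling flexibility in the second session.
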